#### 4.5.4 Blood pressure

The pre- and post-dialysis blood pressures during each dialysis session will be summarized by the weighted average to account for the unequal number of dialysis sessions per participant. The differences in overall mean and slope over the study period between treatment arms will be compared using linear mixed effects models to account for both participants within the same facility and repeated measurements within the same participant.

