# 2.2. Secondary Objectives

# 2.2.1. Secondary Effectiveness Objectives

Secondary objectives of the TiME Trial are to determine whether thrice weekly hemodialysis with session durations of at least 4.25 hours:

- 1. Improves blood pressure control
- 2. Reduces the incidence of post-dialysis hypotension
- 3. Reduces inter-dialytic fluid intake
- 4. Maintains or improves adherence to dialysis treatments
- 5. Has benefits that are linked to rate of fluid removal (ultra-filtration rate)

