# **Inclusion Criteria**

- 1. Initiation of maintenance dialysis within the past 120 days.
- 2. Treatment with maintenance dialysis in a participating facility.
- 3. Age ≥18 years.

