#### 4.5. Intervention

Dialysis facilities randomized to the Intervention arm will adopt an approach of recommending that all patients who are initiating treatment with maintenance hemodialysis have a treatment session duration of at least 4.25 hours even if urea clearance and fluid removal are considered adequate with shorter treatment durations.

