# 4.7.2.3. Other Secondary Effectiveness Outcomes

Pre-dialysis blood pressure, post-dialysis blood pressure, and inter-dialytic weight gain are secondary outcomes that will be used to evaluate the hypothesis that longer dialysis treatment sessions improves blood pressure control, reduces intra-dialytic hypotension, and reduces post-dialysis fluid intake because of less hemodynamic instability. Dialysis attendance will be compared between treatment groups to determine the effect of longer prescribed session duration on adherence to scheduled dialysis treatments.

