#### Dialysis treatment data

- 1. Session length (delivered): every session
- 2. Pre-dialysis weight: every session
- 3. Post-dialysis weight: every session
- 4. Pre-dialysis systolic and diastolic blood pressure: every session
- 5. Post-dialysis systolic and diastolic blood pressure: every session
- 7. Vascular access type (presence or absence of catheter): once per month

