A major objective of the trial is to evaluate effectiveness of the intervention for the overall population of patients receiving maintenance hemodialysis rather than to evaluate efficacy of the intervention for a selected, non-representative subset. Because the randomized treatment assignment for the dialysis facility will be determined before patients are enrolled, a requirement for patient-level informed consent would likely result in important differences in the characteristics of participants in the two treatment groups (intervention patients would be those who *a priori* are interested in having longer dialysis sessions and the usual care cohort would be "all comers"). These differences would substantially undermine the objectives of the TiME Trial.

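### SAP 4.5.4 compares mean blood pressure between arms without adjusting for any baseline reading, although pre-dialysis pressure is collected at every session

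*Combined protocol and SAP*

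**What the plan says.** Protocol 2.2.1 lists as its first secondary effectiveness objective that longer sessions "Improves blood pressure control". Protocol 4.7.2.3 gives the outcomes: "Pre-dialysis blood pressure, post-dialysis blood pressure, and inter-dialytic weight gain are secondary outcomes".

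SAP 4.5.4 has the readings from each session "summarized by the weighted average to account for the unequal number of dialysis sessions per participant", and then: "The differences in overall mean and slope over the study period between treatment arms will be compared using linear mixed effects models". The model accounts for facility and for repeated readings within a participant. No baseline value, change score or baseline covariate is named.

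Protocol 4.8 collects "Pre-dialysis systolic and diastolic blood pressure: every session", so an early reading exists in both arms.

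The other places where an adjustment might be found do not supply one:

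- Protocol 6.3 and the Analytic Approach row of the summary table provide adjustment for unbalanced covariates, but for mortality.
- SAP 4.1 refers to a generic multivariable linear model and lists no covariates.
- SAP 4.2 describes and compares baseline balance but adjusts nothing.
- SAP 4.5.2 does define a baseline window for quality of life and analyses change from it. Blood pressure has no counterpart.

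**The concern.** The objective is about improvement, but an unadjusted study-period mean mixes where patients started with what happened afterwards. Two things are at stake for the mean comparison.

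The first is precision. Stable between-patient differences in pressure that an early reading would explain stay in the error term.

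The second is entry imbalance. Protocol 5.3.1 notes that "the randomized treatment assignment for the dialysis facility will be determined before patients are enrolled", and the information sheet that offers the opt-out differs by arm. Randomization is stratified by provider, catheter use and race (protocol 4.4), not by blood pressure. If the arms enrol somewhat different patients, a lasting difference in their usual pressure would appear as a treatment difference.

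**Working it through.** **Inputs.** From protocol 6.2.1: 256 facilities, 4,250 participants in the primary analysis population, cluster-size SD 10 or 16. The documents give no SD, ICC, correlation or detectable difference for blood pressure, so there is no figure of the plan's own to reproduce. The following are assumptions: correlation r of 0.3 to 0.6 between the first pre-dialysis reading and the follow-up mean, SD 15 to 25 mmHg, and ICC 0.01 to 0.05.

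**Step 1: precision.** Adjustment multiplies patient-level variance by 1 − r² and interval width by √(1 − r²).

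| r | Variance removed (r²) | Width factor | Narrowing |
|---|---|---|---|
| 0.3 | 9% | 0.954 | 5% |
| 0.4 | 16% | 0.917 | 8% |
| 0.5 | 25% | 0.866 | 13% |
| 0.6 | 36% | 0.800 | 20% |

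These figures are at patient level. How much of the gain reaches the facility-clustered interval depends on the ICC.

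**Step 2: chance imbalance in the first reading.** Mean cluster size m = 4250/256 = 16.6. The design effect is DE = 1 + ((1 + CV²)m − 1) × ICC, where CV is the cluster-size SD divided by m, and SE = SD × √(4 × DE/4250).

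- Low end (cluster-size SD 10, ICC 0.01, SD 15): DE = 1.22, SE = 0.51, 95% range about ±1.0 mmHg.
- High end (cluster-size SD 16, ICC 0.05, SD 25): DE = 2.55, SE = 1.23, 95% range about ±2.4 mmHg.

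This spread is already part of the standard error of a correctly clustered model. It widens the interval but does not bias the estimate.

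**Step 3: a persistent entry difference.** A simulation (400 replicates) used 256 facilities of 17 patients with 30 monthly values each and no treatment effect. The assumed SDs were facility 4, patient 15, noise in the first reading 14, noise in each monthly value 6 (all mmHg), and patient slope 0.25 mmHg per month. The resulting correlation was about 0.72.

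| Quantity | Unadjusted | Adjusted for first reading |
|---|---|---|
| SE of mean difference (mmHg) | 0.68 | 0.39 |
| Mean difference with a 2 mmHg entry difference built in | 2.02 | 0.90 |
| Slope difference, same setting | about 0 | about 0 |
| SE of slope difference (mmHg per month) | 0.008 | 0.008 |

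The 0.90 agrees with direct arithmetic. The stable share of the first reading's variance is (4² + 15²)/(4² + 15² + 14²) = 241/437 = 0.55, so 2 × (1 − 0.55) = 0.90 remains.

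The simulated correlation lies above the 0.3 to 0.6 range, and the ICC of the stable level (16/241 = 0.07) lies above 0.05. The fall from 0.68 to 0.39 therefore illustrates the direction of the gain and is not a forecast of its size.

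**The case against.** The case for leaving the section alone has real content.

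- Blood pressure is one of the other secondary outcomes, with no power target. Omitting a precision covariate does not invalidate a randomized comparison. This stands and limits the weight of the point.
- A reader might infer that chance imbalance between arms biases the result. It does not, because facilities are randomized and the clustered standard error covers it.
- A reader might infer that the whole quoted analysis is affected. The slope is not: a constant starting difference goes into the intercept, as Step 3 shows. The slope does not rescue the mean comparison, however, since it would miss an early shift that is then sustained.
- The clause on allocation before enrolment comes from the argument for waiving consent. Enrolling all eligible patients unless they opt out (SAP 1) is the plan's own protection against entry imbalance, and nothing in the documents shows that opt-out differed by arm. The risk is reduced but not removed, because allocation precedes entry and the information sheets differ.
- A reader might take the first transferred pre-dialysis reading to be free of all trial influence. The documents do not say so. It precedes that session's treatment, but entry requires only "Initiation of maintenance dialysis within the past 120 days", and intervention facilities are "recommending that all patients who are initiating treatment with maintenance hemodialysis have a treatment session duration of at least 4.25 hours". No section states that the first transferred session is the first one under the facility's approach. If it is not, the reading is partly post-exposure, and adjusting for it could slightly attenuate the effect.
- Blood pressure is absent from the list of study-entry items in protocol 4.8, but that list covers demographic and comorbidity data. Pressure is collected with the treatment data, so there is no gap in collection. Averaging one early reading into a long series also matters little in itself. The weakness is that it is not used as a covariate.

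**Conclusion.** The point holds for the overall-mean comparison. SAP 4.5.4 leaves out a baseline adjustment that the collected data allow. The cost is patient-level intervals about 5% to 20% wider than the same intervals after adjustment would be, taking the adjusted width as a share of the unadjusted (r of 0.3 to 0.6, assumed), with an unknown share of that reaching the clustered interval. Any persistent entry difference also passes in full into the mean: 2 mmHg in, about 2 mmHg out. Adjustment for one noisy reading removes only part of this, leaving 0.90 of 2 mmHg under the simulated variances.

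The documents do not show that such an entry difference exists, and they do not support a claim that the slope is compromised or that chance imbalance is a source of bias. With a secondary outcome and a nearly free repair, this is a worthwhile improvement to the SAP and does not threaten the trial's main conclusions.

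**What to change.** In SAP 4.5.4:

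1. Define baseline as the pre-dialysis systolic and diastolic reading at the first transferred session, and remove it from the outcome series.
2. Enter it as a covariate in the overall-mean mixed models for both pre- and post-dialysis pressure. The first post-dialysis reading already follows a session, so it should not serve as its own baseline.
3. Confirm and state when that session falls relative to the participant's first session under the facility's approach.
4. Keep the unadjusted mean as a sensitivity analysis, in case the reading is partly post-exposure.

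In SAP 4.2, tabulate the baseline reading by arm.

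The slope comparison needs no change. The cost is a few sentences and one reading per participant out of the outcome series; the values are already transferred. Two small downsides should be stated in the SAP: a single reading corrects an entry imbalance only in part, and some attenuation is possible if exposure began before the first transferred session.

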#### 4.5.5 Ultrafiltration rate

Ultrafiltration rates for each dialysis session will be calculated as milliliters of fluid removed per kilogram body weight per hour (ml/kg/hr). The ultrafiltration rates will be summarized by the weighted average to account for the unequal number of dialysis sessions per participant. The differences in overall mean and slope over the study period between treatment arms will be compared using linear mixed effects models to account for both participants within the same facility and repeated measurements within the same participant.

#### **5** Loss to Follow-Up

Given the nature of end-stage renal disease and dialysis practices, it is possible that loss-to-follow-up will be above the anticipated loss-to-follow up rate of 5% per year due to transfer of care and kidney

transplantation. Extensive efforts will be made to collect complete mortality data. If a participant transfers his/her care to a non-participating dialysis facility that is within the same dialysis provider organization, all data elements for the patient will continue to be included in the data transfers from the dialysis provider organization.

For the primary analyses of mortality, participants will be censored at the time of loss to follow-up, which can lead to bias if censoring is informative – i.e., the censoring mechanism is associated positively or negatively with survival. The major projected source of censoring is receipt of a kidney transplant, which tends to occur in healthier patients with a relatively good prognosis. The potential implications of censoring of participants who undergo kidney transplantation will be explored by estimating the cumulative incidence of both death and kidney transplantation. For the secondary quality of life outcomes, missing data may be anticipated due to death, loss to follow-up for transplant and other reasons, and dependence on participants completing the questionnaires. In secondary analyses, different strategies will be used to handle missing data due to loss-to-follow-up and death. For the former, comparisons will be made between participants with complete follow-up and those lost to follow-up, with respect to observed characteristics, and discrepancies will be pursued to shed light on the reasons for missing data in subjects with incomplete follow-up. Inverse probability weighting (IPW) will be used when fitting models.
